5.5.1 Acceptable Concomitant Medications

All treatments that the investigator considers necessary for a subject's welfare may be administered at the discretion of the investigator in keeping with the community standards of medical care. All concomitant medication will be recorded on the case report form (CRF) including all prescription, over-the-counter (OTC), herbal supplements, and IV medications and fluids. If changes occur during the trial period, documentation of drug dosage, frequency, route, and date may also be included on the CRF.

All concomitant medications received within 28 days before the first dose of trial treatment and 30 days after the last dose of trial treatment should be recorded. Concomitant medications administered after 30 days after the last dose of trial treatment should be recorded for SAEs and ECIs as defined in Section 7.2.

5.5.2 Prohibited Concomitant Medication

Subjects are prohibited from receiving the following therapies during the Screening and Treatment Phase (including retreatment for post-complete response relapse) of this trial:

- Antineoplastic systemic chemotherapy or biological therapy
- Immunotherapy not specified in this protocol
- Chemotherapy not specified in this protocol
- Investigational agents other than pembrolizumab
- Radiation therapy
 - Note: Radiation therapy to a symptomatic solitary lesion or to the brain may be allowed after consultation with Sponsor (except during screening).
- Live vaccines within 30 days prior to the first dose of trial treatment and while participating in the trial. Examples of live vaccines include, but are not limited to, the following: measles, mumps, rubella, varicella/zoster, yellow fever, rabies, BCG, and typhoid vaccine. Seasonal influenza vaccines for injection are generally killed virus vaccines and are allowed; however, intranasal influenza vaccines (eg, FluMist[®]) are live attenuated vaccines and are not allowed.

- Glucocorticoids for any purpose other than to modulate symptoms from an event of clinical interest (ECI) of suspected immunologic etiology or from symptomatic brain metastasis(es) [also during whole brain radiation therapy (WBRT)]. The use of physiologic doses of corticosteroids may be approved after consultation with the Sponsor.
 - *Note: Inhaled steroids are allowed for management of asthma.*
 - *Note: Use of prophylactic corticosteroids to avoid allergic reactions (e.g., to IV contrast dye) is permitted.*

Subjects who, in the assessment by the investigator, require the use of any of the aforementioned treatments for clinical management should be removed from the trial. Subjects may receive other medications that the investigator deems to be medically necessary.

The Exclusion Criteria describes other medications which are prohibited in this trial.

There are no prohibited therapies during the Post-Treatment Follow-up Phase.

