After treatment discontinuation, each subject will be followed for 30 days for adverse event monitoring [serious adverse events (SAEs) and events of clinical interest (ECIs) will be collected for 90 days after the end of treatment or until the patient initiates new anticancer therapy, but for at least 30 days after the end of treatment, whichever is earlier]. Subjects who discontinue for reasons other than disease progression will have post-treatment follow-up for disease status every 9 weeks (± 7 days) in the first year and every 12 weeks (84 ± 7 days) after year 1 until disease progression is confirmed by the Investigator/local radiology review, a non-study cancer treatment is initiated, consent is withdrawn, death, becoming lost to follow-up, or the end of study. After trial discontinuation, all subjects will be followed by telephone for overall survival (OS) approximately every 12 weeks or more frequently as requested by the Sponsor until death, consent is withdrawn, becoming lost to follow-up, or the end of study.

This study will be conducted in conformance with Good Clinical Practices.

Specific procedures to be performed during the trial, as well as their prescribed times and associated visit windows, are outlined in the Trial Flow Chart - Section 6.0. Details of each procedure are provided in Section 7.0 – Trial Procedures.

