5.5 Concomitant Medications/Vaccinations (Allowed & Prohibited)

Medications or vaccinations specifically prohibited in the exclusion criteria are not allowed during the ongoing trial. If there is a clinical indication for any medication or vaccination specifically prohibited during the trial, discontinuation from trial therapy or vaccination may be required. The investigator should discuss any questions regarding this with the Sponsor Clinical Director. The final decision on any supportive therapy or vaccination rests with the investigator and/or the subject's primary physician. However, the decision to continue the subject on trial therapy or vaccination schedule requires the mutual agreement of the investigator, the Sponsor and the subject.

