5.8 Subject Withdrawal/Discontinuation Criteria

Subjects may withdraw consent at any time for any reason or be dropped from the trial at the discretion of the investigator should any untoward effect occur. In addition, a subject may be withdrawn by the investigator or the Sponsor if enrollment into the trial is inappropriate, the trial plan is violated, or for administrative and/or other safety reasons. Specific details regarding discontinuation or withdrawal procedures; including specific details regarding withdrawal from Future Biomedical Research, are provided in Section 7.1.4 – Other Procedures.

In this trial, a subject may discontinue from treatment but continue to participate in the regularly scheduled activities, as long as the subject does not withdraw consent. Once a subject has discontinued treatment, even though he/she continues to be monitored in the trial, he/she may be allowed to begin treatment again if deemed medically appropriate.

A subject must be discontinued from the trial for any of the following reasons:

- The subject or legal representative (such as a parent or legal guardian) withdraws consent.
- The subject is lost to follow-up

A subject must be discontinued from treatment (but should continue to be monitored in the trial) for any of the following reasons:

- The subject or legal representative (such as a parent or legal guardian) withdraws consent for treatment
- Confirmed radiographic disease progression per the terms outlined in Section 7.1.2.6.5

Note: For unconfirmed radiographic disease progression, please see Section 7.1.2.6.5

- Unacceptable adverse experiences as described in Section 5.2.1.2
- Any progression or recurrence of any malignancy, or any occurrence of another malignancy that requires active treatment
- Intercurrent illness other than another malignancy, as noted above, that prevents further administration of treatment
- Recurrent Grade 2 pneumonitis
- Investigator's decision to withdraw the subject from study treatment
- The subject has a confirmed positive serum pregnancy test

- Noncompliance with trial treatment or procedure requirements
- Completed 24 months of treatment with pembrolizumab

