Note: 24 months of study medication is calculated from the date of first dose. Subjects who stop pembrolizumab after 24 months may be eligible for up to one year of additional study treatment if they progress after stopping study treatment at 24 months provided they meet the requirements detailed in Section 7.1.5.2.1.

- Administrative reasons

The End of Treatment and Follow-up visit procedures are listed in Section 6 (Protocol Flow Chart) and Section 7.1.5 (Visit Requirements). After the end of treatment, each subject will be followed for 30 days for adverse event monitoring (serious adverse events and events of clinical interest will be collected for 90 days after the end of treatment or 30 days after the end of treatment if the subject initiates new anticancer therapy, whichever is earlier, as described in Section 7.2.3.1). Subjects who discontinue for reasons other than progressive disease will have post-treatment follow-up for disease status until disease progression, initiating a non-study cancer treatment, withdrawing consent or becoming lost to follow-up. After documented disease progression each subject will be followed by telephone for overall survival until death, withdrawal of consent, or the end of the study, whichever occurs first.

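### The closing sentence of Section 5.5.2 removes subjects from the trial where Sections 5.5 and 5.8 only stop treatment, so some imaging could end before progression

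*Combined protocol and SAP*

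**What the plan says.** Section 5.5.2 lists treatments prohibited during screening and treatment: systemic anti-cancer agents, radiation, live vaccines and glucocorticoids. Some entries carry exceptions. The radiation note reads "Radiation therapy to a symptomatic solitary lesion or to the brain may be allowed after consultation with Sponsor (except during screening"). The glucocorticoid entry allows use for immune-related events, symptomatic brain metastases, asthma inhalers and contrast prophylaxis. The closing sentence then says that subjects who "require the use of any of the aforementioned treatments for clinical management should be removed from the trial".

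Two other sections deal with the same situation differently:

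- Section 5.5: where a prohibited medication is indicated, "discontinuation from trial therapy or vaccination may be required". Continuing on trial therapy is a matter for agreement between investigator, Sponsor and subject.
- Section 5.8: leaving the trial is mandatory only for withdrawal of consent or loss to follow-up. A second list opens "A subject must be discontinued from treatment (but should continue to be monitored in the trial) for any of the following reasons", and it includes "Noncompliance with trial treatment or procedure requirements". The section adds: "Subjects who discontinue for reasons other than progressive disease will have post-treatment follow-up for disease status until disease progression", or until a non-study cancer treatment starts.

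For analysis, Table 9 censors DOR at the last adequate assessment when there is no progression or death, and Table 10 censors PFS at the last assessment. The supplemental SAP repeats both rules in its Tables 1 and 2.

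**The concern.** Leaving treatment and leaving the trial have different consequences for the data. Under 5.8, a subject who stops drug without progression is still scanned until progression. A subject taken out of the trial has no scheduled scans, so an unseen progression becomes a censored time.

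This matters most for radiation. A subject who needs it for a symptomatic lesion may well be close to progression. Censoring at that point would be informative and would make PFS and DOR look longer. For DCR the error runs the other way: a subject with stable disease who is removed before a scan at or beyond 24 weeks cannot meet the criterion.

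DOR, DCR and PFS are key secondary endpoints of an open-label, single-arm study. Whether such a subject is scanned or censored should not depend on which of two sentences a site applies.

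**Working it through.** **Where the closing sentence changes anything**

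| Listed treatment | What the other rules give | What the closing sentence adds |
|---|---|---|
| Chemotherapy, biological therapy, immunotherapy, investigational anti-cancer agents | Imaging ends at new anti-cancer treatment (6.1 note b, 7.1.2.6.2), and Table 9 censors DOR before it | Nothing of substance |
| Radiation agreed under the note | Subject stays on study and is scanned | Loss of scans, if the note is not read as an exception |
| Other radiation | 5.8: stop drug, scan to progression, unless it counts as new anti-cancer therapy (not defined) | Loss of scans, if it is not so counted |
| Glucocorticoids outside the exceptions; live vaccines | 5.8: stop drug, scan to progression | Loss of scans |

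The added loss is confined to the last three rows. Needing a live vaccine is not a sign of worsening, so informative censoring is mainly a question for radiation.

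**Illustration for PFS**

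The plan gives no figure to reproduce and no frequency of removal.

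- From the documents: median PFS of 2 to 3 months in this setting (4.2.1); 2.7 months for second-line single-agent chemotherapy (Table 1); scans every 9 weeks (7.1.2.6.2); n = 160, 93 and 55 (8.2.7).
- Assumed: exponential PFS; 4.348 weeks per month; a share f = 2%, 5% or 10% of progressions preceded by removal; each removed subject censored at the previous scan.

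The chance of progression per scan interval is h = 1 − 0.5^(9/(4.348m)), where m is the median in months. Two scans (weeks 9 and 18) fall before 6 months, so 6-month PFS = (1 − h)². With removal, h′ = h(1 − f)/(1 − hf), and the estimate becomes (1 − h′)².

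| Median | h | f = 0 | 2% | 5% | 10% |
|---|---|---|---|---|---|
| 2 months | 0.512 | 23.8% | 24.3% | 25.1% | 26.5% |
| 2.7 months | 0.412 | 34.5% | 35.1% | 36.0% | 37.6% |
| 3 months | 0.380 | 38.4% | 39.0% | 39.9% | 41.5% |

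The rise is 0.5 to 3.1 points. At a median of 2.7 months the standard error is √(0.345 × 0.655/160) = 3.8 points at n = 160 and √(0.345 × 0.655/55) = 6.4 points at n = 55. The shares correspond to about 160 × 0.655 × f = 2.1, 5.2 and 10.5 removals by week 18.

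**Illustration for DOR**

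Table 11 uses 11 responders among 55 and 24 among 160; the event counts here are assumed. With 11 responders and 4 progressions by month 6, the estimate is 7/11 = 63.6%. If one of the four is censored before the other events, it is 7/10 = 70.0%. With 24 responders and 9 progressions, 15/24 = 62.5% becomes 15/23 = 65.2%.

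**DCR**

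On a 9-week schedule the first scan at or after 24 weeks is week 27. Each subject removed earlier who would have stayed stable costs 100/160 = 0.6 points, 100/93 = 1.1 points or 100/55 = 1.8 points.

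**The case against.** The strongest reply is that the protocol uses 'trial' and 'study' loosely and plainly intends follow-up. Section 5.7.3 has a pregnant subject removed from the study, yet 5.8 lists pregnancy under treatment discontinuation. Section 5.5.2 itself ends by referring to a post-treatment follow-up phase. The radiation note is most naturally a specific exception to a general ban. This makes the literal outcome less likely. It does not correct the sentence, which gives a site an instruction without any such qualification.

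Several limits on the consequence stand:

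- **A scan is still due.** Note z of 6.1 calls for imaging at treatment discontinuation without progression, unless a scan was done in the previous 4 weeks, and 7.1.4.1 asks for final-visit activities on withdrawal from the trial. A subject near progression is the one this scan may catch. If it caught half, the 10% case at a median of 2.7 months would fall to the 5% case, 36.0% (+1.5 points).
- **Deaths may still count.** PFS includes death and has no missed-assessment rule, so PFS censoring is likely but not certain. For DOR, death after two or more missed assessments is censored.
- **Section 2.1 does not restrict follow-up to telephone calls.** A reader might infer that from "After trial discontinuation, all subjects will be followed by telephone for overall survival (OS) approximately every 12 weeks". But the text does not say telephone contact is all there is, and the preceding sentence gives scans to subjects who stop for reasons other than progression.

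A reader might also see a conflict between allowing brain radiation on study and excluding CNS metastases at entry. That does not support this point. A new brain metastasis is progression, not censoring before it, and 7.1.2.6.5 with Table 6 largely covers continuing, stopping and restarting treatment after progression.

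**Conclusion.** The contradiction is real and sits in current text: 5.5.2 orders removal from the trial, while 5.5 and 5.8 provide for stopping treatment with continued monitoring. Read literally, it ends scheduled imaging early for off-list glucocorticoids, live vaccines and radiation not counted as new anti-cancer therapy, including Sponsor-agreed radiation if the note is not taken as an exception.

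It is tempting to conclude that PFS and DOR will be materially inflated. The documents do not support that. The frequency is unknown, and the modelled 0.5 to 3.1 points on 6-month PFS assumes that every removal loses its progression. The result is below one standard error even at n = 160. DOR is more sensitive because responders are few, but those event counts are invented for illustration. ORR changes only if removal precedes a documented response, when the subject counts as a non-responder. Sample size, confidence-interval methods and interim rules are unaffected. This is a minor correction, worth making because it is cheap and removes a rule that can lose endpoint data.

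**What to change.** Replace the closing sentence of 5.5.2 with: *Subjects who require a listed treatment, other than uses allowed in the notes above, should be discontinued from trial treatment and followed under Sections 5.8 and 7.1.5.3.3, with imaging until progression or new anti-cancer therapy.*

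The cost is one wording change and a few extra scans. Some of those scans may partly reflect the non-permitted treatment. That is limited because imaging still ends at new anti-cancer therapy.

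I would not go further and declare that agreed radiation is never new anti-cancer therapy. Shrinkage of an irradiated lesion could then be credited to pembrolizumab, and that question needs its own decision.

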5.6 Rescue Medications & Supportive Care

Subjects should receive appropriate supportive care measures as deemed necessary by the treating investigator. Suggested supportive care measures for the management of adverse events with potential immunologic etiology are outlined along with the dose modification guidelines in Section 5.2.1.2 (Table 4) and in greater detail in the ECI guidance document. Where appropriate, these guidelines include the use of oral or intravenous treatment with corticosteroids as well as additional anti-inflammatory agents if symptoms do not improve with administration of corticosteroids. Note that several courses of steroid tapering may be necessary as symptoms may worsen when the steroid dose is decreased. For each disorder, attempts should be made to rule out other causes such as metastatic disease or bacterial or viral infection, which might require additional supportive care. The treatment guidelines are intended to be applied when the investigator determines the events to be related to pembrolizumab.

Note: if after the evaluation the event is determined not to be related, the investigator is instructed to follow the ECI reporting guidance but does not need to follow the treatment guidance (as outlined in the ECI guidance document). Refer to Section 5.2.1 for dose modification.

It may be necessary to perform conditional procedures such as bronchoscopy, endoscopy, or skin photography as part of evaluation of the event. Suggested conditional procedures, as appropriate, can be found in the ECI guidance document.

Table 5 below shows treatment guidelines for subjects who experience an infusion reaction associated with administration of pembrolizumab.

Table 5 Infusion Reaction Treatment Guidelines

NCI CTCAE Grade	Treatment	Premedication at Subsequent Dosing

Grade 1 Mild reaction; infusion interruption not indicated; intervention not indicated
	
Increase monitoring of vital signs as medically indicated until the subject is deemed medically stable in the opinion of the investigator.
	
None


Grade 2 Requires therapy or infusion interruption but responds promptly to symptomatic treatment (e.g., antihistamines, NSAIDS, narcotics, IV fluids); prophylactic medications indicated for <=24 hrs
	
Stop Infusion and monitor symptoms. Additional appropriate medical therapy may include but is not limited to: IV fluids Antihistamines NSAIDS Acetaminophen Narcotics Increase monitoring of vital signs as medically indicated until the subject is deemed medically stable in the opinion of the investigator. If symptoms resolve within one hour of stopping drug infusion, the infusion may be restarted at 50% of the original infusion rate (e.g., from 100 mL/hr to 50 mL/hr). Otherwise dosing will be held until symptoms resolve and the subject should be premedicated for the next scheduled dose. Subjects who develop Grade 2 toxicity despite adequate premedication should be permanently discontinued from further trial treatment administration.
	
Subject may be premedicated 1.5h (± 30 minutes) prior to infusion of pembrolizumab (MK-3475) with: Diphenhydramine 50 mg po (or equivalent dose of antihistamine). Acetaminophen 500-1000 mg po (or equivalent dose of antipyretic).

Grades 3 or 4 Grade 3: Prolonged (i.e., not rapidly responsive to symptomatic medication and/or brief interruption of infusion); recurrence of symptoms following initial improvement; hospitalization indicated for other clinical sequelae (e.g., renal impairment, pulmonary infiltrates) Grade 4: Life-threatening; pressor or ventilatory support indicated
	
Stop Infusion. Additional appropriate medical therapy may include but is not limited to: IV fluids Antihistamines NSAIDS Acetaminophen Narcotics Oxygen Pressors Corticosteroids Epinephrine ** Increase monitoring of vital signs as medically indicated until the subject is deemed medically stable in the opinion of the investigator. Hospitalization may be indicated. **In cases of anaphylaxis, epinephrine should be used immediately. Subject is permanently discontinued from further trial treatment administration.
	
No subsequent dosing

Appropriate resuscitation equipment should be available in the room and a physician readily available during the period of drug administration. For further information, please refer to the Common Terminology Criteria for Adverse Events v4.0 (CTCAE) at http://ctep.cancer.gov
		

5.7 Diet/Activity/Other Considerations

5.7.1 Diet

Subjects should maintain a normal diet unless modifications are required to manage an AE such as diarrhea, nausea or vomiting.

5.7.2 Contraception

Pembrolizumab may have adverse effects on a fetus in utero. Furthermore, it is not known if pembrolizumab has transient adverse effects on the composition of sperm. Non-pregnant, non-breast-feeding women may be enrolled if they are willing to use 2 methods of birth control or are considered highly unlikely to conceive. Highly unlikely to conceive is defined as 1) surgically sterilized, or 2) postmenopausal (a woman who is ≥ 45 years of age and has not had menses for greater than 1 year will be considered postmenopausal), or 3) not heterosexually active for the duration of the study. The two birth control methods can either be two barrier methods or a barrier method plus a hormonal method to prevent pregnancy. Subjects should start using birth control from study Visit 1 throughout the study period up to 120 days after the last dose of study therapy.

The following are considered adequate barrier methods of contraception: diaphragm, condom (by the partner), copper intrauterine device, sponge, or spermicide as per local regulations or guidelines. Appropriate hormonal contraceptives will include any registered and marketed contraceptive agent that contains an estrogen and/or a progestational agent (including oral, subcutaneous, intrauterine, or intramuscular agents).

Note: Abstinence is acceptable if this is the usual lifestyle and preferred contraception for the subject.

Subjects should be informed that taking the study medication may involve unknown risks to the fetus (unborn baby) if pregnancy were to occur during the study. In order to participate in the study they must adhere to the contraception requirement (described above) for the duration of the study and during the follow-up period defined in section 7.2.2-Reporting of Pregnancy and Lactation to the Sponsor. If there is any question that a subject will not reliably comply with the requirements for contraception, that subject should not be entered into the study.

